Can we enhance the effects of rTMS on motor cortex? A different brain stimulation modality, cervically implanted vagus nerve stimulation (cVNS) can enhance neuroplasticity and facilitate rehabilitation, especially when paired with an intervention such as task-specific training(19, 20). There is a new noninvasive form of this method, transcutaneous auricular vagus nerve stimulation (taVNS). This may also facilitate plasticity and is being investigated in the enhancement of motor learning and recovery in a specific paired fashion. The timing of the paired VNS is critical to the desired neuroplastic changes(21-23), as the behavioral effects of paired therapy disappear when behavior is not intricately synchronized with stimulation. Could pairing taVNS with TMS boost the effects of TMS on cortex, and potentially emerge as a stroke recovery tool? As a first step in this direction, we propose a basic, mechanistic pilot study exploring the use of paired taVNS/TMS to further enhance motor cortex excitability in 24 healthy individuals in a 4 visit, randomized, sham controlled, counterbalanced study.

**Aim 1. Determine the effects of taVNS on motor cortex excitability.** We hypothesize that taVNS alone (sham rTMS + active taVNS) will induce increases in motor cortex excitability (post-stimulation compared to baseline). We believe these changes will be of a lesser magnitude than those of TMS alone (active rTMS + sham taVNS) due to the indirect mechanistic approach of taVNS.

**Aim 2. Determine whether taVNS-paired TMS is more effective at inducing cortical excitability than TMS alone.** We hypothesize that pairing two forms of neuromodulation (active rTMS + active taVNS) will increase TMS-induced cortical excitability in the motor cortex when compared to single modality approaches (active rTMS + sham taVNS; sham rTMS + active taVNS). Furthermore, we believe this increase is timing sensitive, and the paired approach will induce larger TMS-induced cortical excitability compared to unpaired neuromodulation (active taVNS + active taVNS).

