The research team is poised to develop a unique, novel, multimodal form of brain stimulation – combining both taVNS and TMS in a time dependent, synchronized manner. We plan to develop this taVNS/TMS system as Aim 1 of this proposal. Critical to understanding the facilitatory effects of pairing taVNS with TMS is the underlying principle of timing the paired stimulus which be better understood. Aim 2 explores the timing effects of paired taVNS/TMS in a classic MEP paradigm, which can help elucidate whether paring of stimulation is critical to the excitability changes. This proposal aims to create a concurrent taVNS/TMS system that can administer both paired- and unpaired- taVNS/TMS stimulation to the motor cortex and facilitate cortical excitability. We will subsequently use this system to investigate whether the timing of taVNS is critical to inducing motor cortex excitability.

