#### **Pairing taVNS with TMS might synergistically increase the effects of TMS alone**

[figure not shown]
Rat models of VNS-paired therapy have demonstrated that timing is critical to the neuroplastic effects of VNS. Rehabilitation training without VNS takes a long time, and VNS alone fails to restore the behavior without the paired training. Delivering VNS immediately following training fails to enhance the training. Therefore, it is important to synchronize stimulation precisely with the paired training.

Aim 1 of this proposal establishes a computerized system that can synchronize two forms of neuromodulation – TMS and taVNS. Using this system, we will investigate whether the timing of taVNS impacts the cortical excitability effects of TMS alone.

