### Stimulation Parameters.

**rTMS:** 20 Hz rTMS will be delivered (using Magventure X100 system) to the motor hot spot of the left M1

region at 90% of rMT for 2.5 seconds ON and 10 seconds OFF. This will be repeated 40 times, for a total of 2,000 pulses of stimulation over 20-minutes. The stimulation target will be digitally marked using Brainsight neuronavigation for inter- and intra-session targeting validation.

**taVNS:** taVNS will be delivered (using a Digitimer constant current stimulation system) at the optimal stimulation parameters determined by our group (25Hz, 500us pulse width, 200% perceptual threshold) targeting the left anterior wall of the ear canal at a 50% duty cycle for 20 minutes.

**Paired taVNS/TMS:** We will synchronize taVNS with rTMS using MATLAB written software (Figure 2a). This software will deliver active/sham taVNS (25Hz, 500us PW, 200%PT) concurrently with active/sham 20Hz rTMS (2.5s ON, 10s OFF, 90% rMT) targeting the left M1 region (Figure 2b).

**Unpaired taVNS/TMS:** In this condition, active 20Hz rTMS (2.5s ON, 10s OFF, 90% rMT) will be delivered with active taVNS will be delivered in 2.5s trains during the rTMS using MATLAB written software. This software will deliver taVNS (25Hz, 500us PW, 200%PT) concurrently with 20Hz rTMS (2.5s ON, 10s OFF, 90% rMT) (Figure 2b).

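### Aim 2 tests timing by paired versus unpaired stimulation but does not name unpaired versus TMS alone, so the timing result could be misread

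*Combined protocol and SAP*

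**What the plan says.** The heading question of Aim 2 (Section 1.0) is "Determine whether taVNS-paired TMS is more effective at inducing cortical excitability than TMS alone". The hypothesis beneath it compares the paired condition with each modality alone: "when compared to single modality approaches (active rTMS + sham taVNS; sham rTMS + active taVNS". A further sentence covers timing and compares paired only with unpaired: "Furthermore, we believe this increase is timing sensitive, and the paired approach will induce larger TMS-induced cortical excitability compared to unpaired neuromodulation". The bracket after that sentence lists active taVNS twice; I read it as active rTMS plus active taVNS.

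Section 2.0 asks more than this. Its overview says the timing experiment is one "which can help elucidate whether paring of stimulation is critical to the excitability changes". Under the heading on synergistic effects it says: "Using this system, we will investigate whether the timing of taVNS impacts the cortical excitability effects of TMS alone".

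The only analysis given is in the power paragraph of Section 11.0: a one-way ANOVA at 80% power and 5% significance, based on a partial eta of 0.06. It lists no follow-up contrasts and no rule linking the two Aim 2 hypotheses.

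The unpaired condition is described in two ways. Section 3.0 contrasts concurrent (paired) with independent (unpaired) delivery. Section 10.0, Stimulation Parameters, says of the unpaired condition that "active taVNS will be delivered in 2.5s trains during the rTMS using MATLAB written software", and then that it runs concurrently with the rTMS.

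**The concern.** Four conditions follow from the Aims: TMS alone (T), taVNS alone, paired (P) and unpaired (U). The timing hypothesis is about P minus U. That difference equals (P − T) − (U − T), and the plan names P − T but not U − T. Two questions therefore stay open even when both Aim 2 hypotheses succeed.

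- Is pairing critical, meaning U adds nothing to T, or only better, meaning U also adds but less?
- Is the whole of P − U a gain from pairing, or is part of it a fall below TMS alone under unpaired stimulation?

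Section 2.0 makes TMS alone the reference for the timing question, so these are the trial's own questions. The study is described as a first step towards a stroke recovery tool. Later work would be designed differently if synchrony is essential than if taVNS helps at either timing.

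**Working it through.** **Inputs from the documents.** 24 participants in a four-visit, within-subject, counterbalanced design (Sections 1.0 and 10.0); 5% significance, 80% power and partial eta 0.06 (Section 11.0).

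**Assumptions.** The documents give no SD, no within-person correlation and no contrast tests. I take the SD of one person's difference between any two conditions as 1 (unit SD per condition, correlation 0.5), with two-sided 5% paired t tests.

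**The plan's own figure.** Read 0.06 as partial eta-squared: f² = 0.06/0.94 = 0.0638, f = 0.253. For a repeated-measures ANOVA with k = 4, N = 24 and correlation 0.5, λ = N·k·f²/(1 − ρ) = 24 × 4 × 0.0638/0.5 = 12.3 on 3 and 69 degrees of freedom. Power is 82.6%, so 80% is reproduced. It depends on the unstated correlation: 67% at 0.3 and 97% at 0.7. This test concerns any difference among conditions, not timing.

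**Power of one contrast.** Power = P(t with 23 df and noncentrality d√24 exceeds 2.069). At d = 0.6, 0.6 × 4.899 = 2.94 and power is 80%. At d = 0.3 it is 29%.

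**Scenarios.** Simulated chance of a significant result, with means in SD units relative to T:

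| P − T | U − T | P > U | P > T | both | U − T contrast |
|---|---|---|---|---|---|
| +1.2 | +0.6 | 80% | nearly 100% | 80% | U > T: 80% |
| +0.6 | 0 | 80% | 80% | 69% | no effect |
| +0.3 | −0.3 | 80% | 29% | 27% | U < T: 29% |
| 0 | −0.6 | 80% | 2.5% | 2.5% | U < T: 80% |

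P > U is significant in 80% of trials in every row, because P − U is 0.6 SD throughout. In the first row both Aim 2 hypotheses succeed in about 80% of trials and pairing looks critical, although U also exceeds T by 0.6 SD; the unnamed contrast would show that gain with 80% power. In the third row half of the P − U difference is loss (0.3 of 0.6), and no named contrast measures it.

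**Are these sizes plausible against the plan?** With taVNS alone placed at the centre of the other means, the first row has variance (0.6² + 0.6²)/4 = 0.18, so eta-squared is at least 0.18/1.18 = 0.15. That is well above 0.06, though Section 11.0 calls 0.06 the low end of a range. The third row has variance (0.3² + 0.3²)/4 = 0.045, so eta-squared is at least 0.045/1.045 = 0.043, below the planning value.

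**Precision of the added contrast.** The 95% CI half-width is 2.069/√24 = 0.42 SD. If U truly equals T, the chance that the CI excludes a gain of 0.6 SD is 80%, by symmetry with the power at d = 0.6. For 0.3 SD it is 29%.

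**The case against.** **Interference reported as enhancement.** A reader might infer from the last row of the table that a fall under unpaired stimulation would be reported as a timing-sensitive increase. The documents do not support that. In "Furthermore, we believe this increase is timing sensitive, and the paired approach will induce larger TMS-induced cortical excitability compared to unpaired neuromodulation" the words about the increase refer back to paired over the single modalities, and paired versus TMS alone is the heading comparison of Aim 2. A reader who requires both results makes that error in about 2.5% of trials. What stands is that no rule requires both, and that the first and third rows are not resolved even when both are required.

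**Out-of-phase delivery.** It is also tempting to call the unpaired taVNS out of phase or badly timed. The text does not say so: Section 10.0 places it during the rTMS, and Section 3.0 calls it independent.

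**No basis for harm.** Section 1.0 says the behavioural effects of VNS disappear without synchrony, and Section 2.0 says VNS given after training fails to enhance it. That predicts no added benefit, not loss. This is fair, and the negative values are illustrations only. But a prediction of no added benefit is itself a statement about unpaired versus TMS alone, which is not named for testing.

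**Hypotheses are not a contrast list.** Aim 2 is prose, and Section 11.0 specifies no follow-up contrast of any kind, so the gap is not peculiar to this one. True. A contrast chosen after seeing the data would still be weaker support for a mechanistic claim than a planned one.

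**Pilot status.** This is a small mechanistic study in healthy people. That limits the weight of the point but not the case for a change this cheap.

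**Conclusion.** The point holds as a gap in the planned comparisons. Timing rests on paired versus unpaired, and unpaired versus TMS alone is not named although Section 2.0 needs it. The timing result could be misread; the documents do not show that it would be. Under the stated assumptions, both Aim 2 hypotheses can succeed in about 80% of trials while unpaired taVNS also adds to TMS. In the mixed case, paired beats unpaired in about 80% with half the difference due to loss.

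The percentages depend on assumed effects in SD units, equal SDs of the differences, and unadjusted two-sided 5% tests. The logical gap does not depend on them, and it does not change the sample size. No contrast involving the unpaired condition can be interpreted until its two descriptions agree.

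**What to change.** 1. Reconcile Section 3.0 with Section 10.0, Stimulation Parameters, so that the unpaired condition has one definition.
2. Add unpaired versus TMS alone as a planned within-subject contrast, reported with its 95% CI beside paired versus TMS alone.
3. State that a timing-sensitive increase is claimed only if paired exceeds both TMS alone and unpaired. This makes the existing Aim 2 wording binding.
4. Do not call pairing critical if unpaired exceeds TMS alone, or if the CI for unpaired minus TMS alone does not exclude a gain judged meaningful in advance. In those cases say that paired was better than unpaired.

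The margin in step 4 must be set beforehand. Using the observed paired gain as the margin does not work: the condition (U − T) + t·SE < (P − T) reduces to P − U > t·SE, because T cancels. In simulation it agreed with the paired-versus-unpaired test in 92% of trials. In the +1.2/+0.6 case it allowed the word critical in 80% of trials, including about 63% of all trials in which unpaired was also significantly above TMS alone.

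**Cost.** A few lines of text and one contrast, with no new participants, visits or measurements. Requiring both results lowers the chance of a true timing claim from 80% to 69% when paired exceeds both comparators by 0.6 SD. With a CI half-width of about 0.42 SD, calling pairing critical will often be out of reach for a small margin. If the four Aim 2 contrasts are Bonferroni-adjusted, the difference detectable with 80% power rises from 0.60 to 0.73 SD (0.71 for three).

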#### **Pairing taVNS with TMS**

Aim 1 of this study will establish a computerized system that facilitates the intricately timed paring of TMS and taVNS in healthy individuals. High frequency rTMS is a safe form of neuromodulation that is FDA-approved for depression and OCD. High-frequency TMS delivered to the motor cortex has been demonstrated to facilitate cortical plasticity.

taVNS is a safe form of cranial nerve stimulation that has been developed at MUSC by the PI of this project and is actively being used in several MUSC clinical trials exploring its use as a potential treatment for neuropsychiatric disorders. taVNS is also an enhancer of neuroplasticity.

This study will combine two safe, validated forms of neuromodulation delivered either concurrently (paired) or independently (unpaired).

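### Aim 2 is worded two ways, its unpaired comparator is mislabelled, and nothing in the plan says which contrast decides it

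*Combined protocol and SAP*

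**What the plan says.** **Section 1.0, Objectives / Specific Aims.** The first aim reads "Aim 1. Determine the effects of taVNS on motor cortex excitability". The second is headed "Determine whether taVNS-paired TMS is more effective at inducing cortical excitability than TMS alone". Its hypothesis then sets paired stimulation against two comparators, "when compared to single modality approaches (active rTMS + sham taVNS; sham rTMS + active taVNS". A further sentence adds that the gain should depend on timing, and states that comparison as "compared to unpaired neuromodulation (active taVNS + active taVNS".

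**Section 2.0, Background.** Here the first aim is engineering work: "We plan to develop this taVNS/TMS system as Aim 1 of this proposal". The second aim becomes the timing question: "Aim 2 explores the timing effects of paired taVNS/TMS in a classic MEP paradigm". A later Background subsection repeats the engineering version of Aim 1: "Aim 1 of this proposal establishes a computerized system that can synchronize two forms of neuromodulation".

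**Section 3.0, Pairing taVNS with TMS.** Again, "Aim 1 of this study will establish a computerized system that facilitates the intricately timed paring of TMS and taVNS".

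**Section 10.0, Stimulation Parameters.** The unpaired condition is active 20 Hz rTMS with active taVNS. Its taVNS is described as given during the rTMS and concurrently with it; the paired condition is also described as concurrent.

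**Section 11.0, Power Calculation.** One test is named, a one-way ANOVA at 80% power and 5% significance, with an effect size derived from 0.06 partial eta. No section names a primary contrast, a deciding post-stimulation time point or a multiplicity rule.

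**The concern.** Two questions compete for the name Aim 2. Paired against TMS alone asks whether adding taVNS helps. Paired against unpaired asks whether synchronising it matters. The answers can differ: taVNS may help whatever its timing, or paired may beat unpaired without beating TMS alone. If the deciding contrast is not fixed in advance, either result could be presented as success on Aim 2.

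The comparator label adds a second problem in the very sentence that states the timing hypothesis. Read literally, the comparator contains taVNS twice and no rTMS. Paired minus that condition would differ by the whole rTMS effect as well as by timing, so it could not isolate timing.

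**Working it through.** **1. The Aims side by side**

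| Place | Aim 1 | Aim 2 |
|---|---|---|
| Section 1.0 | Effect of taVNS on excitability | Paired vs TMS alone; also vs taVNS alone; then timing |
| Section 2.0, opening text | Build the system | Timing |
| Section 2.0, last subsection | Build the system | Not mentioned |
| Section 3.0 | Build the system | Not mentioned |

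The alternative Aim 1 appears three times and the alternative Aim 2 once. Section 1.0 already contains the timing contrast, so the disagreement over Aim 2 is about which contrast leads.

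**2. The unpaired label**

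Section 2.0 speaks of paired and unpaired taVNS/TMS. Section 3.0 describes two modalities given together or independently. Section 10.0 lists an unpaired taVNS/TMS condition and specifies both modalities as active. None of these describes a condition with taVNS twice and no rTMS. The Section 1.0 label is the outlier.

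**3. What the stated power covers**

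Inputs: 0.06 read as partial eta-squared (Section 11.0); 24 participants in the randomized phase and four conditions (Section 10.0). Section 11.0 gives no sample size, and no section gives a within-subject correlation, so rho is an assumption, as is sphericity.

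- f² = 0.06 / (1 − 0.06) = 0.0638, so f = 0.253.
- λ = f² × n × m / (1 − rho) = 0.0638 × 24 × 4 / (1 − 0.5) = 12.26, with 3 and 69 degrees of freedom.
- Power of the repeated-measures F test at 5% is 82.6%; 80% power needs n = 23.

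The plan's 80% is therefore roughly reproduced at rho = 0.5. At n = 24, power runs from 50% (rho = 0) to 97% (rho = 0.7). If 0.06 already reflects the within-subject error term (λ = f² × the error degrees of freedom), power is 37%. On any of these readings the figure belongs to the omnibus test of equality among conditions, not to either Aim 2 contrast.

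**4. Error rate with two candidate contrasts**

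Suppose paired vs TMS alone and paired vs unpaired are each tested at two-sided 5% and both are null. The chance of at least one rejection is 1 − P(|Z1| < 1.96 and |Z2| < 1.96), with Z1 and Z2 bivariate normal.

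| Correlation (assumed) | At least one rejection | At least one rejection favouring paired |
|---|---|---|
| 0 | 9.75% | 4.9% |
| 0.3 | 9.5% | 4.8% |
| 0.5 | 9.1% | 4.5% |
| 0.7 | 8.3% | 4.2% |

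A correlation near 0.5 is natural because both contrasts share the paired condition. The last column compares with 2.5% for a single test. With the third Aim 2 contrast (paired vs taVNS alone) added, independent tests would give 1 − 0.95³ = 14.3%.

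**5. Where that excess comes from**

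Section 1.0 on its own already holds all three contrasts. Correcting the Aim wording in Sections 2.0 and 3.0 would leave step 4 unchanged; naming a deciding contrast would not.

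**The case against.** The strongest reply is that this is editorial. Section 1.0 is the designated Aims section, includes both contrasts, and puts TMS alone first. Building the system has no statistical contrast attached. No condition, visit or measurement changes between the two sets of Aims. The comparator label is visibly a slip, and the study calls itself a mechanistic pilot. Most of this stands. A reader might infer that the trial would really run a comparator without rTMS, or that the timing hypothesis is untestable by design. The documents do not support that, since Sections 2.0, 3.0 and 10.0 all give the unpaired condition both modalities. Nor do they show two complete rival sets of Aims, as only one Background sentence restates Aim 2.

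A second reply is that no pairwise tests are specified, so the 9% is hypothetical. That is fair: it is conditional on separate 5% tests. If pairwise tests were allowed only after a significant ANOVA, the error would be held at 5% when all conditions are equal. But the plan states no such gate. Section 1.0 also expects TMS alone to exceed taVNS alone, a difference that could open the gate while both main contrasts were null.

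What does not stand is that the pilot label makes the choice unnecessary. Section 1.0 states directional hypotheses and Section 11.0 claims power for a test, so the contrast that answers Aim 2 should be identifiable.

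**Conclusion.** The point holds in limited form. The Aims are worded inconsistently, one comparator label is wrong as written, and no text says which contrast decides Aim 2. The first two are matters of drafting. The third has statistical content: about a 9% chance of at least one false positive instead of 5%, or about 4.5% instead of 2.5% counting only results that favour paired stimulation. This rests on two separate 5% tests, both null, with an assumed correlation of 0.5. A reader might attribute that excess to the conflicting Aims; it would be there with Section 1.0 alone.

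Correcting the label will not by itself give a clean timing contrast. The Stimulation Parameters text describes both paired and unpaired delivery as concurrent, so the difference between the two conditions must also be reconciled there.

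**What to change.** 1. Use the Section 1.0 Aims throughout. In Sections 2.0 and 3.0, describe building the system as preparatory work, and align the single Background sentence on Aim 2 with Section 1.0.
2. Correct the unpaired label in Section 1.0 so that it contains both active rTMS and active taVNS, and reconcile it with Section 10.0, Stimulation Parameters. The sponsor must state the intended timing.
3. State before data are seen that paired vs TMS alone decides Aim 2, as its heading implies. Test paired vs unpaired next, in fixed order, as the timing question, and only if the first contrast succeeds. Report paired vs taVNS alone as supportive. This order keeps the error for the two main contrasts at 5% without splitting alpha.

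The cost is wording and a prior commitment to one headline contrast; no visit or procedure is added. The sponsor should know that the stated 80% does not carry over to that contrast. With 24 participants, a paired two-sided 5% t test has 80% power at a standardized paired difference of 0.60. If the contrast had the same f = 0.253 (two means differing by 2f = 0.505 SD), its power would be 66% at rho = 0.5, ranging from 39% at rho = 0 to 86% at rho = 0.7.
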